7.2.2 Protection Against Other Minor Procedure/Study Related Risks

- It is expected that some individuals may feel uncomfortable taking cognitive tests; consequently, we will make every effort to ensure subject participant comfort during their neurocognitive testing.
- There will be three blood draws which could potentially produce minimal pain, bruising or discomfort; however, blood draws will be conducted by trained professionals which will minimize any of the above mentioned risks
- Every effort will also be made to ensure the confidentiality of the subject participant, including the use of unique patient identifiers for the study forms, and database entry. The subject binders/data

³ http://www.kdigo.org/clinical_practice_guidelines/pdf/KDIGO%20AKI%20Guideline.pdf

will be kept in a locked cabinet within a locked room which is only accessible to the study team. If any subject contact information is kept digitally, it will be kept in a password protected computer only accessible to authorized study personnel.

7.3 Methods and Timing for Assessing, Recording, and Analyzing Safety Parameters

There are common and significant side effects of statins. The commonest are: headache, difficulty sleeping, flushing of the skin, muscle aches, tenderness, or weakness (myalgia), drowsiness, dizziness, nausea and/or vomiting, abdominal cramping and/or pain, bloating and/or gas, diarrhea, constipation, rash. In addition, statins also carry warnings that memory loss, mental confusion, high blood sugar, and type 2 diabetes are possible side effects. Patients can have elevations of liver transaminase levels. The most significant side effects are: myositis, elevated levels of CPK, or creatine kinase, and rhabdomyolysis. We will evaluate patients for all of these side-effects (73, 74). Guyton describes the risks of severe side-effects as very small (73). "The significant risks pertain to rhabdomyolysis and myopathy." Rhabdomyolysis risk ... is about 3 cases per 100,000 person-years. However, because only 4 cases have been defined thus far, there is no basis for assigning an occurrence rate other than "rare." (74) Statin-attributable peripheral neuropathy incidence of 12 per 100,000 person-years or prevalence of 60 per 100,000 persons. Acute liver failure has occurred in statin users with a spontaneous reporting rate of 0.1 case per 100,000 person-years of treatment. Correction for underreporting might increase this rate to 0.5–1 case per 100,000 person-years, but this is approximately equal to the background rate of liver failure in the general population. There is no evidence that statins cause acute or chronic kidney damage."

At the time that a patient is invited to enroll, we ask about side effects that the patient might have previously had associated with statins, and especially if the side effects occurred at higher doses. Patients will not be enrolled if they had any side effects at their current dose or at higher doses. Since the three statins we will be studying may also interact with other medications, changing either their pharmacokinetic or pharmacodynamics properties (3), we will record other medications and their dosages that patients are taking.

All patients enrolled will have lipid profiles, CBC w/Diff, and comprehensive metabolic panels (including creatinine, LFTs), and CK obtained at several time points to detect any physiologic symptoms associated with the statin intervention. At multiple time points, patients will have a research coordinator or nurse contact them to verify that the patient is complying with their statin regimen as well as to ask questions regarding their subjective experience of taking the statin regimen. Patients will be asked about a variety of symptoms associated, though rarely, with statin use, i.e., myalgias, gastrointestinal distress, arthralgia, etc. (Section 6 Schedule of Assessments).

Patients randomized to maximize their statin regimen or randomized into the atorvastatin 80mg group are the only patients we anticipate having a significant risk of side effects. The Stroke Prevention by Aggressive Reduction in Cholesterol Levels (SPARCL) Investigators study enrolled 4731 patients to be randomized to receive atorvastatin 80mg or placebo(4). The median follow up was 4.9 years. Except for elevations of the liver enzymes ALT and AST, there were no differences between the atorvastatin and placebo groups. Patients in arm 1 and randomized to placebo in arm 2 are at minimal, to no, risk, as their statin regimen will not be changed. Patients randomized to atorvastatin 10mg in arm 3 are at minimal risk of side effects, as they will be started on a new statin regimen, but at a very low dose of a slightly lipophilic statin.

In addition:

- During their CEA hospital stay, the electronic medical chart will be reviewed from admission to discharge and a copy of the admission and discharge notes will be printed for the subject binders and de-identified to be uploaded into the study database.
- The Central Coordinating Center (CCC) will also screen for AEs at all sites while reviewing the data entered and the de-identified Admission/Discharge notes each site must upload to the study database. All study data will be entered into the study database in a timely fashion, no later than 7 days after completion of the follow up unless a safety concern arises and then the report timing must be based on Section 7.6 Reporting Procedures.

7.4 Definition of Adverse Events

- **Adverse events (AE)** will be defined as any symptom, sign, clinically significant abnormal test result, disease, or syndrome occurring during the trial which was either not present at baseline, or if present, worsened during the trial, without any judgment about causality or relationship to the drug.
- **Serious Adverse Event (SAE):** An adverse event will be considered an SAE if it results in any of the following outcomes: death, life-threatening experience, requires or prolongs hospitalization, new significant disability, congenital anomaly or birth defects, or in the opinion of the investigator, other important medical event, whether or not considered related to the participation in the study or not.
- **Non-serious Events (NSAE):** are those adverse events that do not meet the criteria for an SAE, but are still unfavorable medical occurrences in a human study participant, including any abnormal sign (e.g. abnormal physical exam or laboratory finding), symptom, or disease, temporally associated with the participants' involvement in the research.
- **Unexpected Adverse Event (UAE):** adverse AEs not expected from the study drugs being used in the study:
 - Not known side effects of this type of drug in the Package Insert for statins like those being used in the study (i.e. simvastatin, atorvastatin, and/or rosuvastatin).
 - Not listed at the specificity or severity previously observed.
- **Serious, Unexpected and Suspected Adverse Reaction (SUSAR):** serious adverse events that are unexpected and suspected to be related to the study drug must be reported within 15 days to the FDA. These must meet ALL of the following:
 - Serious (S)
 - Unexpected (U)
 - Suspected Adverse Reactions (SAR)

7.5 Reporting Procedures

All AEs will be reported by the local Principal Investigator or designee using the study NSAE/SAE form and based on the Common Terminology Criteria for Adverse Events (CTCAE v.4.03)⁴ for language and severity

⁴ CTCAE_4.03_2010-06-14_QuickReference_8.5x11 <http://evs.nci.nih.gov/ftp1/CTCAE/About.html>

grade criteria. Data regarding timing, seriousness, severity, expectedness, resolution, study drug action taken, if AE resulted in withdrawal from the study, and relationship to the drug along with a preliminary narrative summary will be entered in the NSAE/SAE form. The supporting documentation will also be included with the NSAE/SAE form. All of the AE information will also be entered and uploaded into the study database. The timing of adverse event reporting will correspond to the type of adverse event as noted below (i.e. NSAE, SAE, Unexpected, SUSAR). All semi-annual DSMB/Progress reports will contain details of all NSAEs and SAEs, including any unexpected events or suspected unexpected serious adverse reactions (SUSARs).

In addition to the CTCAE criteria, to screen for acute kidney injury (AKI), we will use the definition provided by the Kidney Diseases Improving Global Outcomes (KDIGO) Clinical Practice Guideline for Acute Kidney Injury (vol 2, issue 1, March, 2012) which states that AKI can be defined by an increase from baseline in serum creatinine (SCr) by 50% within 7 days.³

The Independent Medical Monitor (IMM), [name], will indicate to the Sponsor, Statistical Analysis Center (SAC), and DSMB through [name]/NIA officer whether there are any concerns after review of semi-annual reports. In addition, if the IMM determines that there are any concerns between semi-annual reports or after reviewing SAE reports, the IMM will also notify the Sponsor, SAC, and DSMB, and DSMB ISO through [name]. A teleconference will be conducted with the IMM as needed.

7.5.1 Reporting of Non-Serious Adverse Events (NSAE)

NSAEs will be reported within 48 hours of discovery by the local investigative team to the Coordinating Center by entering the NSAE(s) into the study database. Available de-identified supporting documentation will be included by uploading it to the study database. If further documentation is to be obtained, it will also be uploaded to the study database.

All NSAEs at each site will be reported by the Local Principal Investigator or designee using the NSAE/SAE form. Unless unexpected and/or the events suggest the research places the participants or others at a greater risk of physical or psychological harm that was previously known, the NSAE information will be submitted to the DSMB and ISO/IMM during the semi-annual review. If the NSAE is unexpected and/or the events suggest the research places the participants or others at a greater risk of physical or psychological harm that was previously known, then it will be submitted to the IMM for review within 24 hours from receipt and reported to the IRB, OHRP, and NIA within 2 weeks of receiving the event. In addition, it will also be reported to the other participating sites for their IRB notification.

7.5.2 Reporting of Serious Adverse Events (SAE)

SAEs will be reported within 24 hours of discovery by the local investigative team to the Coordinating Center by entering the SAE(s) into the study database. Available de-identified supporting documentation will be uploaded to the study database. If further documentation is to be obtained, it will also be uploaded to the study database.

The database will email the IMM the list of SAE(s) for him to review and enter his findings within the study database. The database will compile SAEs for the semi-annual DSMB report unless the IMM deems it necessary for the DSMB to review the adverse event before the next semi-annual meeting.

All SAEs at each site will be reported by the Local Principal Investigator or designee using the NSAE/SAE form.

7.5.3 Reporting of Unexpected Serious Adverse Events/Problems (USAE and SUSAR)

All unexpected SAEs/Problems will be reported by the Local Principal Investigator or designee and within 24 hours of discovery to the Central Coordinating Center by entering them into the study database which will immediately trigger emails to [name] (Central PI), [name] (Central Co-PI), [name] (IMM), and [name] (Central Study Coordinator). Available de-identified supporting documentation will be uploaded to the study database. If further documentation is to be obtained, it will also be uploaded to the study database.

The Central Coordinating Center (CCC) will provide the NIA, DSMB Chair, DSMB ISO, Independent Medical Monitor (IMM), and CUMC IRB with the SAE form for the “unexpected event” and supporting documentation within 24 hours of its receipt at the Central Coordinating Center. We will provide any additional information requested and report to the FDA within 15 days. In addition, it will also be reported to the other participating sites for their IRB notification.

Furthermore, if the adverse event is serious, unexpected, and suspected to be associated with the study drug (SUSAR), it will be reported to the NIA, DSMB ISO/IMM, and CUMC IRB within 24 hours of discovery and to the other participating sites so that they can report it to their respective IRBs.

7.6 Follow-up for Adverse Events

Any adverse event that is ongoing when the subject completes or discontinues the study will be followed by the Investigator(s) until the event has resolved, stabilized, or returned to baseline status. The resolution date should be noted on the case report form of the corresponding AE and in the study database.

7.7 Safety Monitoring

As soon as the site’s Principal Investigators become aware of any SAEs, their team must submit corresponding AE reports to the CCC. The CCC will inform the ISO/IMM and DSMB as noted in our DSMP, section 1.2.2 Adverse Event Reporting. The DSMB will meet twice a year, by teleconference call to review study progress, data quality, and participant’s safety.

Safety reports will be sent to the DSMB/ISO/IMM twice a year and will include a detailed analysis of study progress, data and safety issues.

The Principal Investigator (PI) at each site will be responsible for ensuring participants’ safety on a daily basis. The Data and Safety Monitoring Board (DSMB) will act in an advisory capacity to the NIA Director to monitor participant safety, evaluate the progress of the study, to review procedures for maintaining the confidentiality of data, the quality of data collection, management, and analyses.

In addition, we will require that all of the subject’s case report form data to be entered into the study database (eCRFs) within 7 days of generating the data along with any pertinent source documentation, all items scanned per visit and uploaded to the study database. The uploaded documents will be reviewed by the CCC Multisite Coordinator, [name], against the data entered in the study database to

assure for completeness and accuracy of the data in real time. Any queries or concerns will be forwarded to the CCC Principal Investigator, Dr. [name], and as formal queries to each site's coordinator with copy to the corresponding site's Principal Investigator.

Once the subject participant is admitted for the CEA procedure, a de-identified copy of the hospital admission and discharge notes will also be uploaded to the study database and the CCC Multisite Coordinator will review these for adverse events.

Any queries which arise from receipt of the subject data or hospital notes will allow for continuous data and safety monitoring in real time and not just in preparation for DSMB meetings.

The prevalent errors/omissions/queries found through these monitoring reviews will also be addressed generically during our monthly multi-site team calls as part of our continuing study personnel training.

The payment for subject enrollment and participation will be linked to the timely entering of subject data (within 7 days) after each study visit and submission of the corresponding source documentation to the study database. This will ensure our ability to continuously monitor each site for safety, completeness and accuracy of the study data.

[name] and/or his representative will also visit each study site, virtually or in-person, weekly for the first 6 months after their site initiation visit (SIV) and then monthly to insure protocol procedures are followed clearly, consistently, and while keeping patient safety forefront.

There will also be monthly conference calls with all of the sites to make sure that any concerns or questions are addressed and shared with the whole study team. Further visits will be on an as needed basis if a site shows a pattern of study violations and/or have procedural errors that show they need to receive booster training or further study monitoring.

In addition, the data center (SAC) will design the database to evaluate, validate and monitor trial data as part of an ongoing process. The initial validation takes place as early as possible in the data collection process, including real-time validation for range checks, limits on categorical variable entry, checks for completion and consistency, etc. Further error checking, including validation for completeness, is performed when data is posted. Since some errors (in changes over time, and consistency between different forms or scales) cannot be detected on initial data entry, validation checks are performed daily. All data errors and queries are processed promptly. Regular reports to investigators and coordinating centers on accrued data identify unusual or unexpected data points and request that they be confirmed or corrected.

7.7.1 Adjudication of Adverse Events

Prior to DSMB bi-annual meetings, the IMM will review the SAE forms and supporting documentation for all SAEs.

The IMM and the DSMB will make a final determination as to diagnosis, seriousness, expectedness, severity, resolution, and relationship to study drug, based on available narrative summary and supporting documentation. The IMM may request additional information as needed, and the Sponsor will request the

information from the site. If the IMM determines that the treatment assignment of the subject is needed, this information will be provided by the SAC.

The IMM will complete a confirmation (Adverse Event Review form), indicating agreement or disagreement with any of the items in the SAE form. Final adjudicated SAE review forms will be entered into the study database.

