1.2 Secondary Objectives

- 1) To determine whether a pre-operative statin regimen alters the prevalence of early mortality at Day 365 +/- 30.
- 2) To determine whether differences in eCD/dCD identified in Primary Objectives 1- 4 are associated with either:
 - a. levels of, or peri-operative changes in, ESR/CRP, and/or
 - b. changes in either activities of daily living (BLESSED) or cognition (TICS-M) in the year following randomization and surgery.

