7 SAFETY ASSESSMENTS

7.1 Clinical Risks

Patients will have clinical laboratory tests upon enrollment and a research coordinator or nurse will contact them 3 days after starting the study drug to verify the patient's complying with the statin regimen as well as to ask questions regarding their subjective experience of taking the study assigned statin regimen (if the CEA does not occur prior to day 3). If the CEA does happen prior to day 3, the Day of CEA Safety Questionnaire will verify compliance and ask about the subjects experience with the assigned statin regimen. Patients will be asked about a variety of symptoms associated, though rarely, with statin use. According to the FDA, the value of statins has been clearly established yet they also advise that statins,

including the ones which will be part of this study (i.e. simvastatin, atorvastatin and rosuvastatin) offer some rare, but potential risks to statin users:¹

- Hepatic toxicity (indicator symptoms: elevated liver enzymes, bleeding or jaundice)
- Muscle toxicity (indicators symptoms: myalgia and arthralgia)
- Increased glucose levels

In addition, from clinical practice, we also know that statins may produce some minor gastrointestinal discomfort; however, these are minor and mostly tolerated as the benefit of statins tends to outweigh the minor stomach upsets they may produce in some individuals.

Patients randomized to maximize their statin regimen or randomized into the atorvastatin 80mg group are the only patients we anticipate having any risk of side effects.

If a patient reports subjective experiences of side effects, their statin regimen will be modified at the discretion of the caring physician. Although the randomization of the patient is compromised, we will continue to evaluate that patient and proceed with intention to treat principles. If the laboratory values the morning of surgery present with elevations in CK or LFT, their statin regimen will be modified at the discretion of the caring physician.

Other Potential Study Procedure Risks:

- Some people may feel uncomfortable taking cognitive tests.
- Slight pain and/or temporary discoloration of the skin after blood draws.
- Unlikely, but potential breach of confidentiality

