9.2.1 Treatment Assignment Procedures

The randomization design will be stratified by center, previous use of statin and in random blocks of 4 and 6. The randomization process will be supported by the Statistical Analysis Center (SAC) at the Mailman School of Public Health at Columbia University. SAC will provide a central secure web-based randomization data system. All trials supported by the SAC employ central randomization that takes place in real-time. In other words, the patient's treatment assignment is made at the moment of randomization, based on probabilities calculated according to the randomization scheme, and communicated to the recruiting site via a central source (i.e. a secure web site).

- Patients on maximum dose of one of the three statins will be maintained on that dose (ARM 1). This arm will contain 225 participants.

- Those patients on submaximal doses of the 3 study statins will be randomized to their current dose plus placebo or their current dose plus the additional milligrams necessary to bring to raise them to the maximal daily dose of simvastatin (40 mg) or atorvastatin (80 mg) or rosuvastatin (20 mg) depending on which statin they are already on, (ARM 2). There will be 337 participants maintained at their current dose and 338 raised to the maximum dose of their statins.
- If patients are statin naïve, then they will be randomized to either atorvastatin 10 mg or 80 mg daily (ARM 3). ARM 3 will have 50 participants in each arm.

The randomization will be performed automatically by the web-based data system. No one will have access to unblinded treatment information on a regular basis other than the packaging pharmacy. All handling of study medication will take place using blinded bottle codes. It is not expected that serious adverse events will require revelation of treatment assignment, but the study web site will provide for online unblinding in emergencies. Revelation of treatment assignment will be available only to authorized users, who will be required to provide a clinical justification for unblinding. Each case of unblinding will be addressed by study personnel to ensure access to unblinded treatment assignment information is limited, and that such incidents are limited to circumstances where it is necessary for the health of the patient.

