9.4 Outcomes

We have defined our primary outcome on Z-scores based on the mean and standard deviation of cognitive testing change in scores of a surgical reference group before and after surgery (12-25h and 30 days postop/ Day of PO clinical visit).

The cognitive testing has been divided by cognitive domains and the patients are considered to have postoperative early cognitive dysfunction (eCD) based on two criteria to account for both focal and global/hemispheric deficits. Consequently anyone with:

- (a) $\geq 2SD$ worse than reference group in two or more cognitive domains or
- (b) $\geq 1.5SD$ worse than the reference group in all cognitive domains tested will be considered a primary outcome.

If the subjects experience stroke or TIA peri-operatively, they will be considered as having reached a secondary OUTCOME in the study.

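### Section 7.7.1 lets the medical monitor learn a patient's assignment while finalising SAE diagnosis, severity and relatedness, with no blinded determination recorded first

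*Combined protocol and SAP*

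**What the plan says.** Section 7.7.1 covers all SAEs. It states: "The IMM and the DSMB will make a final determination as to diagnosis, seriousness, expectedness, severity, resolution, and relationship to study drug". It continues: "If the IMM determines that the treatment assignment of the subject is needed, this information will be provided by the SAC". The IMM then completes an Adverse Event Review form, agreeing or disagreeing with the items on the site's SAE form, and "Final adjudicated SAE review forms will be entered into the study database".

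The general blinding rule is in Sections 5.2 and 9.2.1. Only the packaging pharmacy has regular access to assignments. Emergency unblinding online needs a clinical justification, and study personnel are to ensure that "such incidents are limited to circumstances where it is necessary for the health of the patient".

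Three other sections bear on what is exposed:

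- Section 9.4: "If the subjects experience stroke or TIA peri-operatively, they will be considered as having reached a secondary OUTCOME in the study".
- Section 7.4 defines an SAE by outcomes that include "death, life-threatening experience, requires or prolongs hospitalization, new significant disability". A stroke that prolongs the stay or disables the patient therefore goes to the IMM.
- Section 7.1 says that patients raised to the maximal dose, or randomized to atorvastatin 80 mg, "are the only patients we anticipate having any risk of side effects".

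**The concern.** Relatedness, expectedness and severity are judgements, and so, at the margin, is the diagnosis of a mild stroke. Blinding the person who makes the final call keeps such judgements comparable between arms. Here that person may ask for the assignment on personal discretion, before completing the form that enters the database. Section 7.1 also gives anyone who knows the arm a directional expectation: side effects belong to the maximal-dose group. Section 7.3 says much the same, with a significant risk anticipated only there.

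The trial names safety in its title and purpose, and Section 3 describes Arms 2 and 3 as double-blind. If the final relatedness call can be made with the assignment known, the blind does not fully protect the adjudicated safety comparison. The same holds for any stroke whose diagnosis is settled in this process.

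**Working it through.** The plan gives no figure for this point, so the main check sets the sections side by side.

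**1. Access.** Section 7.7.1 allows release for adjudication, on the IMM's decision, by the Statistical Analysis Center (SAC). Sections 5.2 and 9.2.1 allow release for the patient's health, with a clinical justification. These are different purposes, and 7.7.1 does not repeat the health limit. It also places this review before the twice-yearly DSMB meetings, so much of it is likely to be retrospective rather than emergency care.

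**2. Order.** Section 7.7.1 sets no explicit order. The release clause stands between the final determination and completion of the form, and nothing prevents release from coming first. That the IMM may classify an event with the assignment known is an inference from this silence.

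**3. What is exposed.**

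| Item | Exposed? | Reason |
|---|---|---|
| SAE relatedness, expectedness, severity | Yes | Finalised under 7.7.1 |
| Stroke or TIA meeting the SAE definition | Diagnosis only | 7.7.1 finalises diagnosis; 9.4 counts the event whatever its relatedness |
| Stroke or TIA reported as non-serious | Not adjudicated under 7.7.1 | 7.7.1 covers SAEs only |
| All-cause mortality at Day 365 (Section 1.2) | No | The fact of death cannot be reclassified |
| Primary eCD/dCD | No | Derived from neuropsychometric Z-scores |
| Arm 1 | Not applicable | Observational |

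**4. Scale, as an illustration.** Section 2.2 gives a peri-operative stroke rate below 1.5%. I assume 0.5% to 1.5%. Expected strokes in Arm 2 (675 patients) are:

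- 675 × 0.005 = 3.4
- 675 × 0.010 = 6.8
- 675 × 0.015 = 10.1

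Take 5 strokes in each group at the top of that range (338 maximal dose, 337 current dose) and remove diagnoses from one group only. The two-sided Fisher exact p-values are:

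| Strokes left in the altered group, v 5 in the other | Altered group: maximal dose | Altered group: current dose |
|---|---|---|
| 5 | 1.00 | 1.00 |
| 4 | 0.75 | 1.00 |
| 3 | 0.50 | 0.72 |
| 2 | 0.29 | 0.45 |
| 1 | 0.12 | 0.22 |
| 0 | 0.03 | 0.06 |

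The counts are small, so each diagnosis carries weight. From an even split, however, one or two changes leave p at 0.50 or above. Only the loss of all five in the maximal-dose group brings p below 0.05.

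**The case against.** The strongest reply is that a blinded assessment already exists. Under Sections 7.5 and 7.5.2 the site enters seriousness, severity, expectedness, relationship and a narrative on the SAE form, within 24 hours of discovery, and the site is blinded unless there was an emergency. The IMM only agrees or disagrees with those items, so the two can be compared. This stands, and it limits the harm. It does not remove it: the final determination belongs to the IMM and the DSMB, and no section says that the site's version is the one used in between-arm summaries.

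A second reply is that Sections 5.2 and 9.2.1 govern emergency unblinding through the website and bar only regular access, so that a case-by-case release to an independent monitor can be read alongside them. That reading is possible, but 7.7.1 does not state it, and the purpose of release differs. An independent monitor may also have a sound safety reason to know the assignment, which the fix must respect.

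A reader might infer more than the documents support:

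- **That the stroke/TIA outcome is decided by the IMM.** No section says that the outcome is taken from the IMM's form, and Sections 9.4 and 9.5 specify no between-arm test of stroke. Chart neurological examinations and uploaded hospital notes also bear on it.
- **That mortality is biased.** Cause and relatedness could be coloured by the assignment, but Day-365 mortality counts deaths.
- **That the DSMB adjudicates unblinded.** Section 7.7.1 names only the IMM as able to ask for the assignment. Whether the DSMB should review individual events is a governance choice, not an error.
- **That non-serious TIAs go unseen.** Section 7.5.1 sends non-serious events to the DSMB and the monitor twice a year, and unexpected or risk-raising ones to the IMM within 24 hours of receipt. They miss only the 7.7.1 adjudication.

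Section 7.7 also refers to a separate data and safety monitoring plan that is not among the documents. It may contain a safeguard.

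**Conclusion.** The concern holds in limited form. Section 7.7.1 lets the IMM obtain the assignment at discretion while finalising SAE judgements, with no blinded determination recorded first, and this does not fit the health-only limit in Sections 5.2 and 9.2.1. The exposure is to adjudicated relatedness, expectedness and severity in Arms 2 and 3, and to stroke diagnoses that pass through SAE adjudication.

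The size of any bias cannot be calculated. It depends on how often the IMM asks, and the documents do not say. Sample size, power and alpha are untouched. The illustration rests on an assumed stroke rate of 0.5% to 1.5% and an even starting split. It shows a sparse outcome, not a result that one or two reclassifications would decide. Change is warranted because the rule as written permits an avoidable weakness in the blind and the remedy is nearly free.

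**What to change.** Amend Section 7.7.1 as follows:

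1. The IMM completes and locks the Adverse Event Review form without the assignment.
2. The SAC releases the assignment only after the lock, or earlier where the patient's health requires it. Every release is logged, and an event released early is flagged.
3. Between-arm summaries of safety and of stroke/TIA use the locked blinded determination.
4. Suspected peri-operative strokes and TIAs, including those reported as non-serious, go through the same blinded form, because stroke/TIA is a secondary outcome.
5. Section 7.7.1 is reconciled with Sections 5.2 and 9.2.1, so that one rule governs who may learn an assignment and why.

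The cost is protocol wording, one lock on an existing database form, a release log at the SAC, and a few more forms for the IMM. No new patients, visits or committee are needed.
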